4.1.6.1.1. Markov Chain Monte Carlo Multiple Imputation (MCMC-MI)

The primary method of handling missing efficacy data relative to the primary estimand will be as follows for both binary and continuous endpoints:

For participants who receive rescue medication (i.e., high-potency TCS or systemic AD treatment, defined in [Appendix 13](#)), or discontinue treatment due to lack of efficacy, set to the participant's baseline value subsequent to this time through Week 16. The MCMC-MI will be used to handle the remaining missing data. Imputation will be conducted within each treatment group independently so the pattern of missing observations in one treatment group cannot influence missing value imputation in another. The SAS PROC MI with MCMC option will be used to conduct the MCMC-MI. The imputation model will include the relevant baseline and post-baseline.

For each imputation process, 25 datasets with imputations will be calculated. The initial seed values are given in the table below. Each complete data set will be analyzed with the specified analysis. The results from these analyses will be combined into a single inference using SAS PROC MIANALYZE.

CMH test statistic will be transformed using the Wilson-Hilferty transformation and then standardized (Ratitch 2013) prior to combining them using SAS PROC MIANALYZE. Details of combining estimates and test statistics for categorial endpoints with multiple imputation can be found in [Appendix 14](#).

For binary responses related to EASI and IGA, the binary response variables will be calculated based on the multiply imputed datasets that have been created. Because the MCMC algorithm is based on the multivariate normal model, imputed values for IGA will not generally be one of the discrete values used in IGA scoring (0, 1, 2, 3, or 4). Therefore, to derive the binary IGA response variable, standard rounding rules will be applied to the imputed values. For example, if a participant has an IGA score imputed as 1.4 (and assuming a Baseline IGA score of 3), the imputed value would be rounded down to 1, and the minimum change from Baseline of 2 would have been met. This participant would be considered a responder.

For derivation of an EASI-75 and EASI-90 response, no rounding will be performed. The imputed Week 16 EASI value will be compared directly to the observed Baseline EASI value to determine whether a reduction of at least 75% or 90% was achieved.

For derivation of the following Itch NRS responses, no rounding will be performed. The imputed Itch NRS value will be compared directly to the observed mean baseline Itch-NRS value to determine whether a response was achieved:

- Percentage of participants with Itch NRS of ≥ 4 -point at Baseline who achieve a ≥ 4 -point reduction from Baseline at Weeks 1, 2, 4, and 16.

Imputation of continuous data will parallel that of binary variable. The imputed values will be used for the following key secondary endpoint:

- Percentage change in EASI score from Baseline to Week 16.

Seed Values for MCMC-MI for Induction Period

Analysis	Seed values
	Lebrikizumab 250 mg Q2W Lebrikizumab 250 mg Q4W Placebo
Proportion of participants achieving IGA score of 0 or 1 with a ≥ 2 -point improvement from baseline at Week 16	180345
Change and percentage change from baseline in EASI score at Week 16. EASI-75 and EASI-90 will leverage imputation from EASI score and therefore use the same seed number.	177100
Change and percentage change in Itch NRS from baseline to Week 16. Proportion of participants achieving at least a 4-point improvement from baseline at Weeks 1, 2, 4, and 16 will leverage imputation from Itch NRS and therefore use the same seed number.	119549

Abbreviations: EASI = Eczema Area and Severity Index score; IGA = Investigator's Global Assessment for AD; MCMC-MI = Markov chain Monte Carlo multiple imputation; NRS = Numeric Rating Scale; Q2W = every 2 weeks; Q4W = every 4 weeks.

4.1.6.1.2. Tipping Point Analyses

The co-primary endpoints of EASI-75 and IGA score of 0 or 1 with ≥ 2 -point improvement from baseline at Week 16 and the following key secondary endpoints: EASI-90 at Week 16 and Itch NRS improvement ≥ 4 -point, at Week 16 will be assessed using the tipping point analysis. For

each of these endpoints, the tipping point analysis will only be conducted if its co-primary or key secondary analyses results are statistically significant.

All participants who use rescue medication or discontinue treatment due to lack of efficacy will be imputed as non-responders. Assumptions on missing data as a result of treatment discontinuation due to reasons other than lack of efficacy or any other intermittent missing data will be varied to investigate if there will be any tipping points.

For all the categorical endpoints described above that will be assessed using tipping point analysis, the following process will be used to determine the tipping point:

- Missing responses in the lebrikizumab groups will be imputed with a range of response probabilities, including probabilities of 0, 0.2, 0.4, 0.6, 0.8, and 1.0.
- For missing responses in the placebo group, a range of response probabilities (for example, probability = 0, 0.2 ... 1.0) will be used to impute the missing values. Multiple imputed dataset will be generated for each response probability.
- Treatment differences between lebrikizumab and placebo are analyzed for each imputed dataset using CMH test (Section 4.1.1). Results across the imputed datasets are aggregated using SAS PROC MIANALYZE in order to compute a p-value for the treatment comparisons for the given response probability. If the probability values do not allow for any variation between the multiple imputed datasets (for example, all missing responses in the placebo and lebrikizumab groups are imputed as responders and non-responders, respectively, i.e., extreme case), then the p-value from the single imputed dataset will be used.

The tipping point is identified as the response probability value within the placebo group that leads to a loss of statistical significance when evaluating lebrikizumab relative to placebo.

For tipping point analyses, the number of imputed data sets will be $m=25$ and the seed values to start the pseudorandom number generator of SAS are given in the table below.

Seed Values for Tipping Point Analysis

Analysis	Seed value
Proportion of participants achieving IGA score of 0 or 1 with a ≥ 2 -point improvement from baseline at Week 16	123470
Proportion of participants achieving EASI-75 and EASI-90 at Week 16	123471
Proportion of participants achieving at least a 4-point improvement from baseline in Itch NRS at Week 16	123472

4.1.6.1.3. Non-responder Imputation

The non-responder imputation (NRI) method will be used to handle missing data relative to the supportive estimand for categorical endpoints (composite). Participants who receive rescue medication (i.e., high-potency TCS or systemic AD treatment, defined in [Appendix 13](#)), or discontinue treatment, will be set to non-response subsequent to this time through Week 16. Intermittent missing values will also be set to non-response.

The non-responder imputation (NRI) method imputes missing values as non-responders and can be justified based on the composite strategy (ICH E9 R1) for handling intercurrent events. In this strategy, participants are defined as responders only if they meet the clinical requirements for

response at the predefined time AND they remain on the assigned study treatment (i.e., not using rescue medications and not having missing values due to other reasons). Failing either criteria by definition makes them non-responders.

Randomized participants without at least 1 post-baseline observation will also be defined as non-responders for all visits for the NRI analysis.

4.1.6.1.4. Mixed-effects Model for Repeated Measures (MMRM)

Mixed-effects model for repeated measures analyses will be performed on continuous endpoints to mitigate the impact of missing data. This approach assumes missing observations are missing-at-random (missingness is related to observed data) and borrows information from participants in the same treatment arm taking into account both the missingness of data through the correlation of the repeated measurements.

The values subsequent to rescue medication use (i.e., high-potency TCS or systemic AD treatment, defined in [Appendix 13](#)) or treatment discontinuation will be made missing before applying the MMRM model. The MMRM model is described in Section [4.1.1](#).

4.1.6.1.5. Last Observation Carried Forward (LOCF)

In this analysis, the values subsequent to rescue medication use (i.e., high-potency TCS or systemic AD treatment, defined in [Appendix 13](#)) or treatment discontinuation will be made missing. All missing values will be imputed using LOCF. Baseline value will be used for imputation if there is no post-baseline observation.

4.1.6.2. Handling of Dropouts or Missing Data for Maintenance Period

For maintenance efficacy analysis relative to the maintenance primary estimand (Hybrid), the method of handling missing data including those as a result of intercurrent events will be MCMC-MI. The description of maintenance MCMC-MI method can be found in Section [4.1.6.2.1](#).

MCMC-MI will also be used to handle missing data relative to the maintenance supportive estimand (Hybrid).

For efficacy analysis relative to the maintenance supportive estimand for categorical endpoints (Composite), missing data including those as a result of intercurrent events will be imputed as non-responder. The description of maintenance NRI can be found in Section [4.1.6.2.2](#).

For efficacy analysis relative to the maintenance supportive estimand for continuous endpoints (Hypothetical), missing data including those as a result of intercurrent events will be imputed using LOCF. The description of maintenance LOCF can be found in Section [4.1.6.2.3](#).

The table below describes the planned imputation methods for efficacy and health outcome endpoints for the Maintenance Period.

Imputation Techniques for Various Variables during Maintenance Period

Type of Endpoints	Efficacy and Health Outcome Endpoints	Estimand (Analysis strategy for Intercurrent Events)	Missing Data Imputation Method (Analysis Method)
Categorical	IGA, EASI, and Itch NRS related categorical endpoints at pre-specified timepoints	Maintenance Primary Estimand (Hybrid)	MCMC-MI (Descriptive statistics)
		Maintenance Supportive Estimand (Hybrid)	MCMC-MI (Descriptive statistics)
		Maintenance Supportive Estimand (Composite)	NRI (Descriptive statistics)
	Remaining categorical endpoints	Maintenance Supportive Estimand (Composite)	NRI (Descriptive statistics)
Continuous	EASI percentage change, Itch NRS percentage change	Maintenance Primary Estimand (Hybrid)	MCMC-MI (Descriptive statistics)
		Maintenance Supportive Estimand (Hybrid)	MCMC-MI (Descriptive statistics)
		Maintenance Supportive Estimand (Hypothetical)	LOCF (Descriptive statistics)
	Remaining continuous endpoints	Maintenance Supportive Estimand (Hypothetical)	LOCF (Descriptive statistics)

Abbreviations: EASI = Eczema Area and Severity Index; IGA = Investigator's Global Assessment for AD; LOCF = last observation carried forward; MCMC-MI = Markov chain Monte Carlo multiple imputation; NRI = Non-Responder Imputation; NRS = Numeric Rating Scale.

4.1.6.2.1. Maintenance Period MCMC-MI

The MCMC-MI will be used to handle missing data relative to the maintenance primary estimand (Hybrid) and the maintenance supportive estimand (Hybrid) for both binary and continuous endpoints. Imputation will be conducted within each treatment group independently so the pattern of missing observations in one treatment group cannot influence missing value imputation in another. The SAS PROC MI with MCMC option will be used to conduct the MCMC-MI. The imputation model will include the relevant baseline and post-baseline.

For each imputation process, 25 datasets with imputations will be calculated. The initial seed values are given in the table below. Each complete data set will be analyzed with the specified

analysis. The results from these analyses will be combined into a single inference using SAS PROC MIANALYZE.

The imputation and analysis will be conducted on the MPP only.

The derivation of binary responses related to EASI, IGA and Itch NRS for the Maintenance Period will follow the derivation for the Induction Period. For the derivation of percentage change from baseline in EASI, the imputed values will be used directly to compare with baseline EASI.

Seed Values for MCMC-MI for Maintenance Period

Analysis	Seed values
	Lebrikizumab 250 mg Q2W
	Lebrikizumab 250 mg Q4W
IGA	12345
EASI	12346
Itch NRS	12347

Abbreviations: EASI = Eczema Area and Severity Index score; IGA = Investigator's Global Assessment for AD; MCMC-MI = Markov chain Monte Carlo multiple imputation; NRS = Numeric Rating Scale; Q2W = every 2 weeks; Q4W=every 4 weeks.

4.1.6.2.2. Maintenance Period NRI

The NRI method will be used to handle missing data relative to the maintenance supportive estimand for categorical endpoints (Composite). Participants who receive rescue medication (i.e., high-potency TCS or systemic AD treatment, defined in [Appendix 13](#)), discontinue treatment, or transfer to escape arm will be set to non-response subsequent to this time through Week 68. Intermittent missing values will also be set to non-response.

Participants without at least 1 post-baseline observation will also be defined as non-responders for all visits for the NRI analysis.

4.1.6.2.3. Maintenance Period LOCF

The LOCF will be used to handle missing data relative to the maintenance supportive estimand for continuous endpoints (Hypothetical). In this analysis, the values subsequent to rescue medication use (i.e., high-potency TCS or systemic AD treatment, defined in [Appendix 13](#)), treatment discontinuation or transfer to escape arm will be made missing. All missing values will be imputed using LOCF. Baseline value will be used for imputation if there is no post-baseline observation.

4.2. Participant Dispositions

The following participant disposition summaries will be provided (details of the analysis populations can be found in Section 3):

- Total number and percentage of participants entering each analysis population.

- The number and percentage of participants who entered the study, failed screening, were randomized at Baseline Visit (Visit 2, Week 0), completed Week 16, completed Week 68, and completed the safety Follow-Up Visit. Summary will be provided by the initial randomized treatment group (Analysis population: Intent-to-Treat [ITT]).
- The number and percentage of participants who completed the study, and the number and percentage of participants who discontinued the study at any time, by the initial randomized treatment group and primary reason for discontinuation (Analysis population: ITT).
- The number and percentage of participants who completed the Induction Period and the number and percentage of participants who discontinued from the Induction Period, by treatment group and primary reason for discontinuation (Analysis population: ITT).
- The number and percentage of participants who completed the Maintenance Period and the number and percentage of participants who discontinued from the Maintenance Period, by treatment group and primary reason for discontinuation (Analysis populations: MPP and MSP), in addition, the number and percentage of participants who entered the escape arm will be summarized for the MPP and the MSP.

All participants who were randomized (that is, in the ITT Population) and discontinued from study treatment during any period from the study will be listed together with the discontinuation reason, and the timing of discontinuation from the study will be reported.

Participant allocation by site will be summarized with number of participants who entered the study, number of ITT participants for each treatment group, number of participants discontinued from study treatment, and number of participants discontinued from the study.

4.3. Primary Endpoints Analysis

4.3.1. Definition of endpoints

The co-primary endpoints are comprised of 2 separate endpoints:

- the proportion of participants achieving EASI-75 at Week 16 in lebrikizumab 250 mg Q2W versus placebo or lebrikizumab 250 mg Q4W versus placebo, and
- the proportion of participants achieving IGA score of 0 or 1 and a reduction of ≥ 2 -points from baseline to Week 16 in lebrikizumab 250 mg Q2W versus placebo or lebrikizumab 250 mg Q4W versus placebo.

Descriptions and derivations of these endpoints are shown in [Appendix 1](#).

4.3.2. Main analytical approach

The primary analysis of the study is to test the co-primary null hypotheses described in Section 2 in the ITT Population.

The primary estimand addresses the treatment response as directed. The analysis assumes that treatment response disappears for participants who took rescue medication (i.e., high-potency TCS or systemic AD treatment, defined in [Appendix 13](#)) or withdrew from the study due to lack of efficacy, therefore setting to the participant's baseline value subsequent to this time through

Week 16. Other missing values will be imputed using MCMC-MI based on missing at random assumption (Section 4.1.6.1.1).

A CMH test as described in Section 4.1.1 will be used for the comparisons. The OR, the corresponding 95% CIs and p-value, as well as the treatment differences and the corresponding 95% CIs, will be reported.

Multiplicity controlled analyses will be performed on the primary and key secondary endpoints to control the overall Type I error rate at a 2-sided alpha level of 0.05. A graphical approach will be used to perform the multiplicity controlled analyses as described in Section 2.1.

The analyses for primary outcomes of EASI-75 and IGA score of 0 or 1 are described in [Appendix 2](#).

4.3.3. Sensitivity Analyses

Sensitivity analyses are included to demonstrate robustness of analyses methods using different missing data imputations and analyses assumptions. Sensitivity analyses for the co-primary endpoints will be conducted using the tipping point analysis based on missing not at random assumption (Section 4.1.6.1.2) described in [Appendix 2](#).

There will be no adjustment for multiple comparisons for additional analyses of the primary outcomes.

4.3.4. Supplementary analyses

Supplementary analyses of the co-primary endpoints will be conducted using supportive estimand (Section 1.1.1.1.2) and different analysis population of PPS (Section 3) described in .

4.4. Secondary Endpoints Analysis

4.4.1. Major secondary endpoints

4.4.1.1. Definition of endpoints

Major secondary endpoints are listed in Section 1.1 under Major Secondary.

Descriptions and derivations of these endpoints are shown in [Appendix 1](#).

4.4.1.2. Main analytical approach

The analyses for the major secondary outcomes are described in [Appendix 2](#).

4.4.1.3. Sensitivity Analyses

Sensitivity analyses for the major secondary endpoints are described in [Appendix 2](#).

4.4.2. Other secondary endpoints

Other secondary endpoints are listed in Section 1.1 under Other Secondary.

Descriptions and derivations of these endpoints are shown in [Appendix 1](#).

The analyses for the other secondary endpoints are described in [Appendix 2](#).

4.5. Tertiary/Exploratory Endpoints Analysis

These analyses may be described in the Exploratory Analyses and Health Technology Analyses Plan.

4.6. Safety Analyses

The planned analyses of safety data will be performed with an intent to maintain consistency with compound level standard safety analyses. These standards are based on internal standards which were informed by Clinical Data Interchange Standards Consortium (CDISC) standards, regulatory guidance (for example, FDA Clinical Review Template), and cross-industry standardization efforts (for example, Pharmaceutical Users Software Exchange [PhUSE] white papers from the Standard Analyses and Code Sharing Working Group provided in the PhUSE Computational Science Deliverables Catalog).

Safety evaluations will be based upon the following safety analysis populations with their associated study periods, unless specified otherwise:

- Safety Population (Induction Period),
- MPP (Maintenance Blinded Period), and
- All Lebrikizumab Safety Population (Combined Induction and Maintenance Periods, and Combined Induction and Maintenance Periods plus Follow-Up Period [selective analyses]).

These analysis populations, treatment groups, associated study periods, and the comparisons for each analysis population are fully defined in Section 3.

For document writing purposes for safety, tests with two-sided p-values less than 0.05 will be referred to as having strong statistical evidence for a treatment difference, unless otherwise noted. However, p-values should not be over-interpreted for these safety analyses. Except for pre-specified hypotheses, they correspond to data-driven hypotheses and hence are only useful as a flagging mechanism.

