### **9.4.4. Safety Analyses**

Safety analyses will include AEs, SAEs, AESI, vital signs, and laboratory analytes. The safety data will be summarized descriptively by treatment group. Categorical safety measures will be summarized with the number and percentage of participants. Continuous safety measures will be

summarized as mean change by visit. Exposure to study intervention will be calculated for each participant and summarized by treatment group.

Adverse events will be coded according to the Medical Dictionary for Regulatory Activities (MedDRA) and summarized by system organ class (SOC), preferred term (PT), severity, and relationship to the study intervention. A TEAE is defined as an event that first occurred or worsened in severity after the baseline period. The baseline period for the Induction Period is defined as the time from the screening visit (Visit 1) to the date/time of the first injection in the Induction Period. Baseline for the Maintenance Period is the events ongoing just prior to the first injection of study intervention at Week 16. The Treatment Period will be used as the postbaseline period for the analysis. For events that are gender specific, the denominator and computation of the percentage will include only participants from the given gender.

The number and percentage of participants who experienced TEAEs, TEAEs by maximum severity, deaths, SAEs, TEAEs related to study intervention, discontinuations from study intervention due to an AE, and AESI will be summarized. Treatment-emergent adverse events (all, by maximum severity), SAEs including deaths, and AEs that lead to study intervention discontinuation will be summarized and analyzed by MedDRA SOC and PT.

Treatment-related TEAEs (TEAEs considered related to study intervention) are defined as events that are indicated by the investigator on the eCRF to be related to treatment.

Adverse events of special interest will be identified by a Standardised MedDRA Query (SMQ) or a Lilly-defined MedDRA PT listing.

Suicide-related thoughts and behaviors occurring during treatment will be summarized based on responses to the C-SSRS consistent with the C-SSRS Scoring and Data Analysis Guide (Columbia Lighthouse Project Scoring and Data Analysis Guide [WWW]).

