Listing of AE (including AEs in the Maintenance Period and the Follow-Up Period)	S

Abbreviations: A = All Lebrikizumab Safety Population; AE = adverse event; ITT = Intent-to-Treat; MPP = Maintenance Primary Population; MSP = Maintenance Secondary Population; PT = Preferred Term; SAE = serious adverse event; S = Safety Population; SOC = System Organ Class; TEAE = treatment-emergent adverse event.

Statistical comparisons will be performed for Safety Population using Fisher's exact test. OR will be provided.

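### The SAP's label for safety tests with p<0.05 conflicts with its own flag-only caveat, and the odds ratio, the only between-group AE measure it states, has no finite value when placebo has no events

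*SAP*

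**What the plan says.** SAP section 4.6 sets a convention for document writing: "tests with two-sided p-values less than 0.05 will be referred to as having strong statistical evidence for a treatment difference", with a closing clause that allows exceptions where they are noted. It continues that "p-values should not be over-interpreted for these safety analyses" and that, pre-specified hypotheses excepted, "they correspond to data-driven hypotheses and hence are only useful as a flagging mechanism".

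The tests concerned are set out elsewhere in the SAP. Section 4.1.1 specifies Fisher's exact test for AEs and other categorical safety measures, with odds ratios of lebrikizumab to placebo. It specifies ANCOVA on treatment and baseline value for continuous laboratory values and vital signs. Section 4.6.2 repeats this for AEs: "Statistical comparisons will be performed for Safety Population" by Fisher's test, and "OR will be provided". It states no confidence interval for the odds ratio, no risk difference and no rule for zero cells. It does require the number and percentage of participants with each event. Section 3 gives the two Induction Period comparisons, Q4W and Q2W each against placebo.

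Error control (SAP 2.1 and 4.3.2) covers only the co-primary and key secondary endpoints. Protocol section 9.4.4 says of safety: "The safety data will be summarized descriptively by treatment group".

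**The concern.** The label and the caveat cannot both guide the author of the study report. A result that is only a flag for medical review is not strong evidence of a difference, yet the label is what would appear in the text. The exception clause does not settle this, because neither document sets out an exception for the laboratory or AE tests. With many unadjusted tests, some laboratory differences will cross 0.05 by chance, and the convention supplies strong wording for them.

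The second issue is estimation. For binary efficacy and health outcome endpoints, SAP 4.1.1 plans a risk difference with a 95% CI. For AEs it plans only an odds ratio, which is infinite when the event occurs on lebrikizumab and not on placebo. An AE seen only on active treatment is a pattern that a safety reader will want to size, and the SAP states no finite between-group estimate for it.

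At stake is how safety findings are described and estimated. Efficacy inference is not touched.

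**Working it through.** The documents give no false-positive figure for safety tests, so there is none to reproduce. The arm sizes used below, 120:80:80, come from SAP section 5. The power stated there (above 95% for Q2W and above 80% for Q4W) does reproduce under exact enumeration of the two-sided Fisher test: 97.9% for IGA and over 99.9% for EASI-75 on Q2W, and 82.5% and 99.1% on Q4W.

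**Laboratory tests**

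- Analytes, counted from protocol Appendix 2: 13 haematology + 20 chemistry + 4 lipids = 37.
- Induction Period tests: 37 × 2 comparisons = 74.
- Expected chance results below 0.05 with no effect: 74 × 0.05 = 3.7. Correlation does not change this expectation.
- Without lipids: 33 × 2 = 66 tests, and 66 × 0.05 = 3.3.
- Probability of at least one, if independent: 1 − 0.95^74 = 0.978.
- The tests are not independent: placebo is shared and some analytes overlap, such as haemoglobin with haematocrit. Simulation with a shared placebo arm and an assumed common correlation between analytes gives:

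| Assumed correlation | P(at least one) |
|---|---|
| 0 | 97% |
| 0.3 | 91% |
| 0.6 | 67% |

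Vital signs, also tested by ANCOVA, would add to the count and are left out here.

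**Adverse events: error rate**

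Fisher's test is conservative for rare events. With the same true rate in both arms, its actual size for Q2W against placebo is 0.3% at a 1% rate and 3.0% at a 5% rate. The chance-finding argument therefore belongs to the laboratory tests and does not carry over to rare AEs.

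**Adverse events: estimate**

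- Probability of no placebo event among 80: 0.99^80 = 0.45 at a true 1% rate; 0.98^80 = 0.20 at 2%.
- An infinite odds ratio also needs at least one event on lebrikizumab. For Q2W, with 1% in both arms: 0.99^80 × (1 − 0.99^120) = 0.31.
- Examples with 0/80 on placebo (risk difference in percentage points, Newcombe interval):

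| Lebrikizumab | Fisher p | Sample OR | Risk difference (95% CI) |
|---|---|---|---|
| Q2W 6/120 | 0.083 | infinite | 5.0 (−0.3 to 10.5) |
| Q2W 7/120 | 0.043 | infinite | 5.8 (0.4 to 11.6) |
| Q4W 5/80 | 0.059 | infinite | 6.3 (0.5 to 13.8) |
| Q4W 6/80 | 0.028 | infinite | 7.5 (1.4 to 15.4) |

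The risk difference is finite in every row. The sample odds ratio is the same in all four and does not distinguish them.

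**The case against.** A reader might infer that the SAP obliges the report to overstate every chance difference. The documents do not support that. The labelling sentence carries an exception clause, and the caveat follows at once, so an author who reads the whole paragraph is told to treat these p-values as flags. Overstatement is a risk created by two conflicting instructions. It is not a certain result of following the plan.

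A reader might also infer that an AE absent on placebo goes unestimated. That is too strong. The tables show the count and percentage per arm, the Fisher p-value is still reported, and an infinite odds ratio still has an exact lower confidence limit (0.99 for 7/120, 1.22 for 6/80). What the SAP lacks is a stated finite contrast. Nor is a zero placebo count the usual outcome at these rates, since 45% and 20% are both below half.

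Other objections have force. The risk difference does not turn 6/120 against 0/80 into a clear finding, because its interval still includes zero; that is a limit of sample size. Uncommon events of interest are also covered by AE and SAE listings and by dedicated tables for infections, conjunctivitis, hypersensitivity, injection site reactions and malignancy. The protocol's descriptive summary does not exclude tests used as flags, and the same section also says that some AE categories will be analysed. Finally, the SAP refers repeatedly to compound level safety standards, which are not available here and may add effect measures or a rule for zero cells.

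Two things remain. The contradictory sentence stands in this SAP whatever the standards contain, and this SAP itself states no finite between-group AE estimate for a zero placebo count.

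**Conclusion.** The point holds in limited form and is minor. In SAP 4.6 the label and the caveat conflict. With no true effect, about 3.7 of some 74 laboratory tests would qualify for the label by chance. The probability of at least one is 98% under independence and about 67% at an assumed correlation of 0.6. These figures rest on a count of 37 analytes from the protocol and two comparisons each; the correlations are assumptions, not figures from the documents.

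Separately, the odds ratio is the only between-group AE measure stated in the SAP, and it is not finite when placebo has no events. The 45% and 20% assume 80 placebo participants and true rates of 1% and 2%. Whether the compound level standards fill this gap cannot be determined from the documents. No primary or key secondary conclusion depends on either issue.

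**What to change.** 1. Replace the labelling sentence in SAP 4.6 with: *Nominal two-sided p<0.05 will be used only to flag findings for medical review, will be labelled unadjusted, and will not be described as strong statistical evidence of a treatment difference.* The caveat that follows can stay, and the two will then agree.
2. In the Safety Population AE tables and other categorical safety tables, add the risk difference with a 95% CI that is valid with zero cells, for example Miettinen-Nurminen or Newcombe, beside the odds ratio.

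The cost is one sentence and an added column in the table program, with no new data. The downside is a small departure from the compound-level table layout. If the compound level standards already provide a risk difference with such an interval, a cross-reference in 4.6.2 is enough for the second change.
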